Cohort 2 includes patients who completed durvalumab monotherapy or in combination with any other approved or investigational anticancer agents in a parent study, without confirmed PD during the period of treatment, and who are potentially eligible for retreatment with durvalumab. The patient should not have received any other approved or investigational anticancer agents since completion of durvalumab treatment. Patients who completed the prespecified duration of treatment with durvalumab in a parent clinical study, who received clinical benefit and then subsequently experienced confirmed PD after completion of planned treatment, will be permitted to restart durvalumab treatment provided they meet the eligibility criteria. If a patient was already retreated with durvalumab in the parent clinical study and retreatment has ended, they are no longer eligible for retreatment in this study. In addition, intervening chemotherapy treatment will not be allowed before retreatment with durvalumab. Cohort 2 patients who will be eligible for future retreatment with durvalumab must agree to reconsenting to start retreatment and meet the eligibility criteria detailed in Sections 5.1 and 5.2. Patients who undergo retreatment will follow assessments as per the SoA for Cohort 1 until confirmed PD, unless unacceptable toxicity, withdrawal of consent, or another discontinuation criterion is met (Table 2). Only 1 course of retreatment is allowed (inclusive of any retreatment in the parent

clinical study). Treatment beyond disease progression is allowed at the Investigator's discretion, if it is in the patient's best interest. The baseline imaging results for Cohort 2 must be available within 28 days of retreatment. While on retreatment, follow-up tumor assessments will be performed according to the Investigator's standard practice (at least every 12 weeks) using RECIST v1.1 (Table 1). Upon discontinuation of durvalumab, patients may receive any subsequent anticancer therapy at the discretion of the Investigator and will follow the SoA detailed for Cohort 3 for safety and survival follow-up (Table 3).

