- k. Patients will receive durvalumab monotherapy until confirmed PD. Section 6.6 details recommendations for patient management after the end of the study.
- l. Results for LFTs, electrolytes, full blood count, and creatinine must be available before commencing an infusion (within 3 days) and reviewed by the treating physician or Investigator prior to dosing.
- m. Disease progression during treatment should be confirmed by the Investigator according to RECIST v1.1 modified for confirmation of progression, as described in [Appendix C](#).
- n. The baseline imaging results from the parent clinical study will be used for baseline tumor assessments for Cohort 1.

Note: All assessments on treatment days are to be performed prior to infusion, unless otherwise indicated.

Cohort 1 will move to SoA for Cohort 3 after durvalumab treatment ends.

AE adverse event; BP blood pressure; C Cycle; CTCAE v5.0 Common Terminology Criteria for Adverse Events version 5.0; ECOG Eastern Cooperative Oncology Group; eCRF electronic case report form; GI gastrointestinal; HBV hepatitis B virus; HCV hepatitis C virus; HIV human immunodeficiency virus; ICF informed consent form; LFT liver function test; PD progressive disease; Q28days every 28 days; Q4W every 4 weeks; RECIST v1.1 Response Evaluation Criteria in Solid Tumors version 1.1; SAE serious adverse event; SoA schedule of activities; SoC standard of care; T3 triiodothyronine; T4 thyroxine; TSH thyroid-stimulating hormone; WHO World Health Organization.

Table 2 Schedule of assessments for patients who completed treatment with durvalumab monotherapy or durvalumab in combination with any other approved or investigational anticancer agents, and are eligible for future retreatment (Cohort 2)

	Follow-up before retreatment				Retreatment					
	Time since the last dose of study drug ^a			Long-term follow-up	Baseline ^b / C1	C2	C3	C4	C5 onwards ^c	
Week	Baseline/ Enrollment ^a	Day (±3 days)	Day (±7 days)		Every 3 months (±2 weeks)	0	Q4W ±3 days unless dosing needs to be held for toxicity reasons			
Day		30	60	90		1	Q28days ±3 days unless dosing needs to be held for toxicity reasons			
Informed consent										
Informed consent	X ^d					X ^e				
Eligibility criteria	X ^d					X ^e				
Study procedures										
Vital signs ^f		X	X	X		X	X	X	X	X
Physical examination ^g		X				X	X	X	X	X
WHO/ECOG performance status						X	X	X	X	X
Concomitant medications		X	X	X		X	X	X	X	X
Laboratory safety assessments										

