Clinical chemistry ^h		X	X	X		X	X	X	X	X
Hematology ^h		X	X	X		X	X	X	X	X
TSH (reflex free T3 or free T4) ⁱ		X	X	X		X	X	X	X	X
Pregnancy test ^j		X				X	X	X	X	X

	Follow-up before retreatment				Retreatment					
	Time since the last dose of study drug ^a			Long-term follow-up	Baseline ^b / C1	C2	C3	C4	C5 onwards ^c	
Week	Baseline/ Enrollment ^a	Day (±3 days)	Day (±7 days)		Every 3 months (±2 weeks)	0	Q4W ±3 days unless dosing needs to be held for toxicity reasons			
Day		30	60	90		1	Q28days ±3 days unless dosing needs to be held for toxicity reasons			
Monitoring										
AE/SAE assessment ^k		X	X	X		Throughout				
Survival status ^l					X					
Study drug administration										
Durvalumab (monotherapy) ^m						X	X	X	X	
Tumor assessment										
Tumor assessment ⁿ	Assessment performed according to the Investigator’s standard practice until withdrawal of consent, progression or death.					X ^o	Assessment performed according to RECIST v1.1 as determined by the Investigator (at least every 12 weeks) until withdrawal of consent, progression or death.			

- a. Follow-up visits are performed based on the duration since the last dose of study drug in either the parent clinical study or current study (whichever most recently administered the study drug). Patients who are more than 90 days beyond the last dose of study drug, will not undergo follow-up for AEs/SAEs, vital signs, concomitant medications, or laboratory safety assessments; these patients will be followed for survival and undergo tumor assessment per Investigator’s standard practice.
- b. Baseline assessments may be performed over more than 1 visit if necessary. If laboratory or imaging procedures were performed for alternate reasons prior to signing the consent, these can be used for baseline assessment purposes with consent of the patient. However, all baseline laboratory assessments must be obtained within 3 days prior to Day 1 (first retreatment visit), and baseline imaging results must be obtained within 28 days prior to Day 1 of retreatment. Baseline laboratory assessments performed within 3 days prior to Day 1 do not need to be repeated at Day 1. Patients with documented HIV test results from the parent clinical study do not need to undergo a repeat test, but HBV and HCV must be retested within the 28-day period.

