- j. For women of childbearing potential only. A urine or serum pregnancy test is acceptable. Women of childbearing potential are required to have a pregnancy test within 7 days prior to the first dose of study drug and then every 4 weeks. Pregnancy test may occur on Day 1 of each cycle, but results must be available and reviewed by the treating physician or Investigator prior to commencing an infusion. A pregnancy test should also be performed 30 days (± 3 days) after last dose of study drug and discontinuation of retreatment (Table 3). Further pregnancy testing after 30 days of treatment discontinuation should be conducted as clinically indicated.
- k. For AEs and SAEs reported during the study, additional information such as concomitant medications will be needed. Medical history previously recorded in the parent clinical study will be made available in the study and does not need to be collected. AE/SAE assessment will be performed according to CTCAE v5.0.
- l. Upon completing the 90-day follow-up for AEs and SAEs, patients will be followed for survival. Survival follow-up will be performed by telephone call (or a prespecified preferred method of contact, as an alternative). Patients will be contacted by telephone in the week following data cut-offs to confirm survival status. No additional retreatment with durvalumab will be allowed.
- m. Results for LFTs, electrolytes, full blood count, and creatinine must be available before commencing an infusion (within 3 days) and reviewed by the treating physician or Investigator prior to dosing.
- n. Disease progression during treatment should be confirmed by the Investigator according to RECIST 1.1 modified for confirmation of progression, as described in Appendix C.
- o. The most recent imaging results from the parent clinical study may be used as the baseline assessment, provided it was obtained within 28 days prior to Day 1.

Note: Cohort 2 will move to SoA for Cohort 3 after retreatment with durvalumab ends.

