- Cohort 2: includes patients who completed durvalumab monotherapy or in combination with any other approved or investigational anticancer agents in a parent study, without confirmed PD during the period of treatment, and who are potentially eligible for retreatment with durvalumab. The patient should not have received any other approved or investigational anticancer agents since completion of durvalumab treatment. Patients who completed the prespecified duration of treatment with durvalumab in a parent clinical study, who received clinical benefit and then subsequently experienced confirmed PD after completion of planned treatment, will be permitted to restart durvalumab treatment provided they meet the eligibility criteria. If a patient was already retreated with durvalumab in the parent clinical study and retreatment has ended, they are no longer eligible for retreatment in this study.
- Cohort 3: includes patients previously treated with durvalumab monotherapy or in combination with any other approved or investigational anticancer agents who are no longer receiving durvalumab and are not eligible to receive retreatment.

Prospective approval of protocol deviations to recruitment and enrollment criteria, also known as protocol waivers or exemptions, is not permitted.

Each patient should meet all of the inclusion criteria and none of the exclusion criteria for this study, to be assigned to a study cohort. Under no circumstances can there be exceptions to this rule. Patients who do not meet the entry requirements are screen failures, refer to Section 5.4.

For procedures for withdrawal of incorrectly enrolled patients see Section 7.3.

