6.1 Treatments administered

6.1.1 Investigational product

AstraZeneca will supply durvalumab (MEDI4736). All patients in Cohort 1 will receive durvalumab monotherapy at the dosing regimen described below (Table 6). While patients in Cohort 2 are all eligible for retreatment with durvalumab, some may never receive treatment. Patients who were previously administered durvalumab at a dose regimen different from the regimen described for the present study will switch to the dose regimen described below. Only 1 course of retreatment is allowed (inclusive of any retreatment in the parent clinical study). Patients enrolled in Cohort 3 will not receive any study drug.

Table 6 Study treatment

	Treatment
Study treatment name:	Durvalumab (MEDI4736)
Dosage formulation:	500-mg vial solution for infusion after dilution, 50 mg/mL
Route of administration:	Intravenous (IV)
Dose:	1500 mg
Dosing instructions:	A dose of 1500 mg will be delivered through an IV administration set with a 0.2 µm or 0.22 µm filter. If a patient’s weight falls to 30 kg or below (≤ 30 kg), then the patient should receive weight-based dosing equivalent to 20 mg/kg of durvalumab q4w until weight improves to above 30 kg (>30 kg).
Packaging and labeling:	Study drug will be provided in vials. Each vial will be labeled in accordance with Good Manufacturing Practice Annex 13 and per country regulatory requirement. ^a
Frequency:	Every 4 weeks
Manufacturer:	MedImmune
Provider:	AstraZeneca

^a Label text prepared for durvalumab (MEDI4736) will show the product name as “MEDI4736” or “durvalumab (MEDI4736)” depending upon the agreed product name used in the approved study master label document. All naming conventions are correct during this transitional period.

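### Protocol Table 2 footnote l can be read as closing first retreatment for Cohort 2 patients in survival follow-up, in conflict with the Cohort 2 rule, and needs reconciling

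*Protocol*

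**What the plan says.** **Footnote l.** In Table 2 of Protocol Section 1.1, the row "Survival status ^l" has a single X. It stands in the long-term follow-up column, inside the block for follow-up before retreatment. The footnote begins "Upon completing the 90-day follow-up for AEs and SAEs, patients will be followed for survival". Two sentences on telephone contact follow, and it closes with "No additional retreatment with durvalumab will be allowed".

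**Other Cohort 2 text.** The Table 2 title describes these patients as having completed treatment "and are eligible for future retreatment (Cohort 2"). Protocol Section 1 says of patients "who received clinical benefit and then subsequently experienced confirmed PD after completion of planned treatment, will be permitted to restart durvalumab treatment", and Section 5 adds the only stated condition: they "will be permitted to restart durvalumab treatment provided they meet the eligibility criteria". Section 6.1.1 sets the cap: "Only 1 course of retreatment is allowed (inclusive of any retreatment in the parent clinical study").

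**Patients past day 90.** Footnote a of Table 2 says "Patients who are more than 90 days beyond the last dose of study drug, will not undergo follow-up for AEs/SAEs" and certain other safety assessments. It keeps them in survival follow-up and tumor assessment, and mentions no loss of eligibility for retreatment.

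**Use in the analysis.** Protocol Section 9.2 (Table 11) and SAP Section 2.1.2 define the response evaluable set as the retreated Cohort 2 patients. ORR and DOR are assessed in that set only.

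**The concern.** A sentence barring retreatment is attached to a cell that describes patients still waiting for it. A site that reads the footnote where it stands could conclude that a Cohort 2 patient who enters survival follow-up has lost the option. A site that works from Sections 1, 5 and 6.1.3 would conclude the opposite for the same patient.

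Protocol Section 8 makes adherence to the schedule of activities mandatory, so the footnote cannot be dismissed as commentary. Two things are at stake. One is whether a given patient is offered retreatment. The other is who enters the response evaluable set, because that set is formed by the act of retreatment. It has no planned size, and both documents already make the ORR and DOR analysis depend on enough patients being retreated. Differing site practice would change both the number and the kind of patient in it: on the restrictive reading, it would hold only patients retreated early after their last dose.

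**Working it through.** The documents give no figure on this point, so the check is mainly a comparison of texts.

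**Step 1. Who is in the cell that carries footnote l?**
- The column lies before retreatment, and the table title is for patients eligible for future retreatment.
- Patients whose retreatment in the parent study has ended cannot be retreated here (Protocol Sections 1, 1.2 and 5). Inclusion criterion 10(b) also requires no earlier retreatment.
- Patients retreated in this study move to the Cohort 3 schedule when retreatment ends (note under Table 2).

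By these rules, the patients in the cell have had no retreatment course. For them the sentence either has no effect or bars a first course.

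**Step 2. Does any other text limit the time to first retreatment?**

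| Place | Limit on time since last dose |
|---|---|
| Protocol Sections 1, 1.2, 5 (Cohort 2) | None stated |
| Protocol Section 5.1, criteria 9 to 11 | None stated |
| Protocol Section 6.1.1 | None; all of Cohort 2 is called eligible, though some may never be treated |
| Protocol Section 6.1.3 | None; only a baseline scan within 28 days before restart |
| Protocol Section 8 | None; 3-monthly survival checks from day 90 are described as part of follow-up before retreatment |
| Table 2, footnote a | None; tumor assessment continues past day 90 |
| SAP Section 2.2, Deviations 1 to 4 | None; no category names a late retreatment |

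**Step 3. Compare the parallel footnote.** Table 3 footnote i matches footnote l except that the retreatment sentence is missing. Table 3 is the schedule retreated patients move to. Section 8 also says that Cohort 2 follow-up before retreatment follows the Cohort 3 schedule. So the same patient in the same phase is covered by two schedules, and only one carries the sentence.

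**Step 4. How many patients could the restrictive reading touch?** The documents give neither a distribution of time from last dose to progression nor an expected number of retreatments. As an illustration only, assume that this time is exponential with median *m* months:

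share progressing after day 90 = 0.5^((90/30.4375)/*m*), where 90/30.4375 = 2.957 months.

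| Assumed median (months) | Exponent | Share after day 90 |
|---|---|---|
| 1 | 2.957 | 13% |
| 2 | 1.478 | 36% |
| 3 | 0.986 | 51% |
| 6 | 0.493 | 71% |
| 12 | 0.246 | 84% |
| 24 | 0.123 | 92% |

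The share passes one half at a median of 2.957 months, about 3 months. These are shares of progressions, not of eligible retreatments, because the other eligibility criteria also apply.

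One group needs no distribution. On the restrictive reading, patients who enroll more than 90 days after their last parent-study dose could never be retreated. Footnote a expressly provides for patients past day 90, but the documents do not say how many there are.

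**The case against.** A reader might infer that footnote l ends retreatment at day 90 and so bars most of the retreatments the study intends. The documents do not support that, for three reasons.

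- **The sentence has no time condition.** The 90-day clause opens the footnote and governs when survival follow-up begins. The word *additional* suggests an earlier retreatment and fits the cap of one course. On that reading nothing conflicts.
- **Table 2 has other text about patients after retreatment.** Footnote a counts from the last dose in the parent or the current study, and for Cohort 2 a current-study dose is a retreatment dose. Footnotes g and j also give instructions for the time after retreatment.
- **Most of the protocol points away from a 90-day bar.** The column heading, the table title, footnote a and Section 8 all treat patients past day 90 as still before retreatment. Footnotes d and e of Table 2 send sites to Sections 5.1 and 5.2 for eligibility.

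It can also be said that the analysis set definition does not change, and that ORR and DOR are secondary, descriptive and untested.

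Much of this stands. It shows that a consistent reading exists, and that *most* depends on an assumed median above about 3 months. It does not remove the ambiguity. Footnotes g and j point expressly to Table 3, whereas footnote l does not say which patients its last sentence covers. The parent-or-current wording of footnote a is repeated in Table 3 footnote a, so it may simply be shared text. Finally, although the set's definition is fixed, its membership depends on how sites read the rule.

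**Conclusion.** The point holds as a wording conflict in operative schedule text. Where footnote l stands, its last sentence has two tenable readings: a bar on first retreatment once survival follow-up starts, or a restatement of the one-course cap. Only the first conflicts with the Cohort 2 passages, and nothing in the footnote excludes it.

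The size cannot be derived from the documents. The 13% to 92% range in the working rests wholly on an assumed exponential time to progression with medians from 1 to 24 months. That later retreatment is open without limit is itself an inference from the absence of a stated interval, subject to the eligibility criteria. The effect on the analysis is confined to who enters the response evaluable set, and so to ORR, DOR and the supporting time to response. The primary safety objective keeps its definition. The correction is worth making because it is cheap and the ambiguity bears on whether patients are offered treatment.

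**What to change.** The sponsor should reconcile footnote l of Table 2 with Protocol Sections 1, 1.2, 5, 5.1, 6.1.1, 6.1.3 and 8 and with Table 3 footnote i. The footnote should say which patients its last sentence applies to, and Tables 2 and 3 should agree. This review does not say which retreatment rule is right.

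The cost is one footnote edit in a protocol amendment. No change to the SAP's set definitions is needed. The Protocol (Section 4.4) expects the study to end in Q4 2022 and the SAP was signed in December 2022, so an amendment may come too late to guide sites. In that case the clinical study report should state which reading sites were told to follow and whether any Cohort 2 patient was refused retreatment because of the footnote. That would let readers judge how the response evaluable set was formed.

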1.2 Synopsis

International Co-ordinating Investigator: PPD
[name]

Protocol Title: An Open-Label, Multi-Center, Global Study to Evaluate Long Term Safety and Efficacy in Patients Who are Receiving or Who Previously Received Durvalumab in Other Protocols (WAVE)

Short Title: Durvalumab Long-Term Safety and Efficacy Study

Rationale: Durvalumab administered either as a single agent or in combination, continues to be evaluated in multiple oncology clinical studies. Durvalumab has been administered intravenously (IV) in multiple clinical studies for up to 12 months or until progressive disease (PD), dependent on the specific protocol. The primary aim of this study is to evaluate the long-term safety and tolerability of durvalumab.

Study Objectives:

The objectives of this study are as follows:

- To monitor long-term safety of durvalumab (all cohorts)
- To assess the efficacy of durvalumab in terms of overall response rate (ORR) and duration of response (DOR) in patients who undergo retreatment with durvalumab (Cohort 2 only)
- To assess the overall survival (OS) of patients (all cohorts)

Overall design: This is a multicenter, open-label, global study that will enroll patients who are currently receiving durvalumab monotherapy, or have previously received durvalumab as monotherapy or in combination with any other approved or investigational anticancer agents, in an eligible AstraZeneca/MedImmune-sponsored clinical study (herein referred to as a parent clinical study).

Patients may enroll under one of three cohorts described as follows:

- Cohort 1: includes patients who received durvalumab monotherapy or durvalumab combination therapy under the parent clinical study (including those undergoing retreatment per the parent study) who have not clinically progressed and who are eligible to continue durvalumab treatment after completing dosing of all other anticancer agents, including other investigational agents, which are a formal component of the parent study. If a patient was already retreated with durvalumab in the parent clinical study and has not progressed while on treatment, then they would be potentially eligible to enter Cohort 1; a combination treatment course initiated in the parent clinical study must be completed prior to study entry.

- Cohort 2: includes patients who completed durvalumab monotherapy or in combination with any other approved or investigational anticancer agents in a parent study, without confirmed PD during the period of treatment, and who are potentially eligible for retreatment with durvalumab. The patient should not have received any other approved or investigational anticancer agents since completion of durvalumab treatment. Patients who completed the prespecified duration of treatment with durvalumab in a parent clinical study, who received clinical benefit and then subsequently experienced confirmed PD after completion of planned treatment, will be permitted to restart durvalumab treatment provided they meet the eligibility criteria. If a patient was already retreated with durvalumab in the parent clinical study and retreatment has ended, they are no longer eligible for retreatment in this study.
- Cohort 3: includes patients previously treated with durvalumab monotherapy or in combination with any other approved or investigational anticancer agents who are no longer receiving durvalumab and are not eligible to receive retreatment.

In addition to providing continued treatment to eligible patients, the study will monitor long-term safety of durvalumab and OS (Cohorts 1 to 3).

Study Period:

Estimated date of first patient enrolled: Q3 2019

Estimated date of last patient visit completed is Q4 2022.

Number of patients: This study will enroll patients who have been previously treated with durvalumab and/or durvalumab in combination with any other approved or investigational anticancer agents at any global site. The study will enroll up to 600 patients. The number of patients is subject to change as new parent studies are included into this long-term safety and efficacy study.

Treatment and treatment duration

Patients in Cohort 1 and those going onto durvalumab retreatment in Cohort 2 will receive durvalumab monotherapy. Patients in Cohort 3 will not receive any study drug.

Durvalumab monotherapy

- Durvalumab 1500 mg via intravenous (IV) infusion every 4 weeks until confirmed PD, unless unacceptable toxicity, withdrawal of consent, death, or another discontinuation criterion is met. Please note, if a patient's weight falls to 30 kg or below (≤ 30 kg), then the patient should receive weight-based dosing equivalent to 20 mg/kg of durvalumab q4w after consultation between Investigator and Study Physician, until the weight improves to above 30 kg (>30 kg).

Duration of treatment

Patients in Cohort 1 will continue to receive treatment with durvalumab until confirmed PD. This includes patients who received durvalumab monotherapy or combination therapy under the parent clinical study, and who are eligible to continue durvalumab treatment after completing dosing of any other approved or investigational anticancer agents, which are a formal component of the parent study.

Continuation with durvalumab monotherapy (Cohort 1) and retreatment with durvalumab monotherapy (Cohort 2) will continue until confirmed PD, unless unacceptable toxicity, withdrawal of consent, death, or another discontinuation criterion is met. Patients will only be eligible for 1 course of retreatment (inclusive of any retreatment in the parent clinical study and this study). Patients will not be eligible to receive retreatment with any other approved or investigational anticancer agents administered in the parent clinical study. Disease progression will be determined by the Investigator following Response Evaluation Criteria in Solid Tumors version 1.1 (RECIST v1.1).

Cohort 3 includes patients who have previously received durvalumab treatment or durvalumab combination therapy and are not eligible for future treatment. These patients will be followed for OS.

Progression during treatment

Patients receiving the study drug who experience disease progression and, in the Investigator's opinion, continue to receive benefits from their assigned treatment; may continue to receive the study drug for as long as they meet specific clinical criteria, and are deriving clinical benefit in the opinion of the Investigator.

For all patients who are treated through progression, the Investigator should ensure that patients still meet all the inclusion criteria and none of the exclusion criteria for this study, and obtain additional informed consent for continuation of treatment. This consent addendum document will be part of the treatment informed consent form (ICF); it will specify that treatment beyond initial evidence of PD is not the standard of care and that alternative treatment options, either locally licensed treatments or other clinical trials, are potentially available for this patient population. Patients with rapid tumor progression or with symptomatic progression that require medical intervention (eg, central nervous system metastasis, respiratory failure due to tumor compression, spinal cord compression) will not be eligible for continuing durvalumab.

Follow up of patients post discontinuation of study drug

Treatment is given until progression, unless there is unacceptable toxicity, withdrawal of consent, or another discontinuation criterion is met. Patients in Cohort 1 who discontinue durvalumab for any reason will not be eligible for further retreatment and will be followed subsequently for safety and survival. All patients in the study will be followed for safety for 90 days after the last dose of durvalumab and for OS and may receive any subsequent anticancer therapy at the discretion of the Investigator. The details of first subsequent anticancer therapy

and overall best response after discontinuation of durvalumab treatment will be collected from the Investigator.

Survival

All patients in the study are followed up for survival every 3 months (± 2 weeks) beginning 90 days after the last dose of the study drug. Patients who enter Cohort 3 are in survival follow-up from the time of enrollment since no study drug is being administered to that cohort. Survival information may be obtained via telephone contact (or a prespecified preferred method of contact, as an alternative) with the patient or the patient's family, or by contact with the patient's current physician.

Statistical methods and endpoints

The primary objective is to monitor long-term safety of durvalumab. The safety analysis set will be used to summarize safety data according to the treatment received for all patients who received at least one dose of durvalumab. This analysis set would include patients continuing study treatment or retreatment, and those who enrolled in this study within 90 days of the last dose of durvalumab or durvalumab combination on the respective parent clinical study. Adverse events (AEs), vital signs and laboratory safety assessments (clinical chemistry, hematology and Thyroid-stimulating hormone [reflex free triiodothyronine or free thyroxine]) will be listed individually by patient. The number of patients experiencing each AE will be summarized by cohort and the National Cancer Institute Common Terminology Criteria for Adverse Events grade (v5.0) (Annex 1).

The analysis set for assessment of efficacy will be based on patients who are retreated with durvalumab in Cohort 2. Efficacy analysis will be performed only if there is sufficient sample size; if so, data may be summarized by tumor type in each tumor type, otherwise, only listings will be provided as descriptive results.

One secondary objective is to assess the efficacy of durvalumab in terms of ORR and DOR for durvalumab retreatment patients. ORR is defined as the number (%) of patients with at a confirmed response of complete response (CR) or partial response (PR). DOR is defined as the time from first documented of CR or PR until the time of first documented disease progression or death in the absence of disease progression since re-initiation of durvalumab treatment. Tumor assessments will be performed by computed tomography scans per standard practice (at least every 12 weeks). Tumor assessments will be performed by the Investigator according to RECIST v1.1; only the response outcomes will be collected in the case report form.

The OS is defined as the time from date of randomization/enrollment in the parent clinical study until the date of death by any cause. A listing of OS data will be provided for all study patients.

In addition, OS and tumor efficacy data in this study may be combined with the parent study data for integrated analysis.

No statistical methods will be employed to test a specific hypothesis in this study. In addition to the 5 planned interim analyses, ad hoc analyses may be performed at various time points in order

to support publications, internal decision making by AstraZeneca, and/or regulatory submissions as appropriate.

[figure not shown]
Sample size estimate

The number of patients enrolled in this study will be determined by the number of patients who received durvalumab and/or durvalumab in combination with any other approved or investigational anticancer agents in original trials, and who wish to participate, and who meet the eligibility criteria. The study will enroll up to 600 patients and the number of patients may change as new parent studies are included into this long-term safety and efficacy study.

